Robertson et al (2007) gave a mean change from baseline in Ki67 of a 2.8% decline and a standard deviation of 22.5% of cells staining for Ki67 for patients receiving fulvestrant 250 mg. In the placebo group they reported a mean reduction and standard deviation of 7.1% +/- 18.0%. There was no significant difference ($p=0.97$) between groups. In the present study, we hypothesize that for women with cyclin D1 overexpression, high dose fulvestrant will have a higher mean reduction in Ki67 than tamoxifen. 58 patients (29 patients in each study treatment arm) will be required to detect a difference between treatments of 15% in cells staining for Ki67 (mean reduction from baseline of 5% for Ki67 level in the tamoxifen group vs. 20% in the fulvestrant group) with power 0.80 for a two-sided test at the 0.05 level. We estimate that 10% of those enrolled to the tamoxifen arm may dropout from the study; however, since fulvestrant is given as a one-time dose, we do not expect attrition from this arm of the study. To account for drop-outs 32 patients will be randomized to each arm.

Treatment assignment

Comparison in the Change of Proliferation Index between Fulvestrant and Tamoxifen in Cyclin D1 +, Estrogen Receptor + Breast Cancer

[name], PI

Essential Elements

#13, 09/13/2017

A total of 64 patients will be randomized in a 1:1 allocation (32 patients to the tamoxifen arm and 32 to the fulvestrant arm) stratified by menopausal status (pre vs. post).. Randomization will be initiated at Mount Sinai by the research pharmacy, using separate randomization lists for pre and post menopausal patients..

Endpoints

Primary endpoint:

- The change in proliferation index between core biopsy and definitive surgery as measured by the percentage of cells staining for Ki67 in each treatment arm, stratified by menopausal status.

Secondary endpoints:

- Determine whether there is a differential treatment effect between tamoxifen and fulvestrant for pre and post menopausal patients.
- The change in estrogen receptor and progesterone receptor levels between core biopsy and definitive surgery in patients treated with fulvestrant or tamoxifen.
- Determine whether tamoxifen-resistance and fulvestrant-sensitivity gene expression signatures are observed in patients with cyclinD1 overexpressing breast cancers.
- Determine whether patient's response to tamoxifen or fulvestrant correlates with the response of their primary cells in vitro.

Data Analysis:

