An intent to treat analysis will be applied to this study. All primary and secondary analysis will be performed, stratified by menopausal status(pre vs. post). Primary continuous response rate of percentage of cells staining for Ki67 between treatment groups will be analyzed using stratified analysis of covariance (ANCOVA). Treatment groups will be compared by stratified analysis of covariance with respect to the outcome variable of post treatment percentage of cells staining for Ki67 with covariate baseline percentage of cells staining for Ki67, allowing for estimation of the mean change from baseline. Assumptions underlying ANCOVA will be evaluated. Transformation of the data will be undertaken if appropriate. A treatment diary will be used for patients enrolled to the tamoxifen arm to record all treatment doses and to help account for any missing data.

A secondary analysis will be a per protocol analysis. Potential interaction will be tested for treatment by stratum (menopausal status) to determine if there exists a differential treatment effect for pre and post menopausal subjects. The mean change in levels (expressed as a percentage of cells staining positive within the breast tumor) of ER (and PR) between pre-treatment and post-treatment will be compared between treatment arms by ANCOVA stratified by menopausal status as in the statistical analysis of the primary objective.

Gene signatures that distinguish cells that are responsive and those that are resistant to tamoxifen have been established using cell lines in vitro. Gene signatures for responsiveness/resistance to fulvestrant have also been established. Presence of these gene signatures will be determined for all patients in this study. Patients having signatures for responsiveness or resistance to tamoxifen (fulvestrant) will be compared with respect to change in Ki67 after treatment with tamoxifen (fulvestrant) by stratified ANCOVA.

Comparison in the Change of Proliferation Index between Fulvestrant and Tamoxifen in Cyclin D1 +, Estrogen Receptor + Breast Cancer

[name], PI

Essential Elements

#13, 09/13/2017

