To determine whether patient's response to tamoxifen or fulvestrant correlated with response in their primary cells in vitro, cells from primary tumors from patients will be grown in vitro. Proliferation assays over a range of doses in vitro, of the same drug that the patient received will be conducted. Correlations between in vitro assay results and patient assay results will be examined by Pearson correlation or Spearman correlation for data not normally distributed for pre- and post-menopausal patients. Dose response will also be analyzed by regression analysis.

Stopping Rule:

Keeping in mind the potential proliferative effect of tamoxifen, this trial will include an early stopping rule, where if the mean change from baseline in the Ki67 proliferation index among the first fourteen patients in the tamoxifen arm is an increase of at least 25%, that arm of the trial will be terminated. Although fulvestrant is unlikely to cause acceleration of proliferation, the same stopping rule will be applied to the fulvestrant arm as well. A mean increase of 25% in 14 patients would give an 80% confidence interval that the true mean Ki67 increase in a treatment arm is in the range of 16% to 34%.

An additional stopping rule will be implemented based on the number of patients experiencing a high level of proliferation (50% or higher). If 2 of the first 10 patients in a treatment arm experience an increase from baseline in the Ki67 proliferation index of 50% or more, then that treatment arm will be terminated.

PATIENT ELIGIBILITY

Inclusion and Exclusion Criteria

Inclusion criteria:

- Written informed consent prior to beginning specific protocol procedures, including expected cooperation of the patients for the study treatment regimen and follow-up, must be obtained and documented according to the local regulatory requirements
- Adult women greater than 18 years of age
- Eastern Cooperative Oncology Group (ECOG) performance status (PS) 0-2
- New diagnosis of invasive cyclin D1 +, ER+, PR +/-, Her2- breast cancer
 - Cyclin D1 positive as defined as a total immunohistochemical score of 5 or greater
 - Hormone receptor positive as defined as $\geq 10\%$ positive stained cells
 - HER2-normal (IHC score 0-1 or FISH negative [in-situ hybridization (ISH) ratio ≤ 2.0 status])
- Tumor size at least 5 mm with planned primary surgery at Mount Sinai
- A negative urine dipstick pregnancy test

Exclusion criteria:

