Both agents in this study (tamoxifen and fulvestrant) have been used extensively in clinical practice with well-known side effects. Likewise both agents have been previously used in the pre-operative setting of a clinical trial (Young 2008). While several studies indicate that tamoxifen does not provide benefit to patients with cyclin D1 positive tumors, the study by Jirstrom et al, actually suggests that tamoxifen may accelerate the growth of tumors (Jirstrom 2005). Pre-clinical data in cell lines supports this conclusion as well. Thus, there is a concern that giving tamoxifen pre-operatively to patients with cyclin D1 positive tumors could accelerate tumor growth. This concern is however limited by two facts; first the length of the treatment in this study is very short and second, tamoxifen is currently used in the neo-adjuvant setting in Europe and less frequently, in the US. Keeping in mind the potential proliferative effect of tamoxifen, this trial will include an early stopping rule, where if the mean change from baseline in the Ki67 proliferation index among the first fourteen patients in the tamoxifen arm is an increase of at least 25%, recruitment of patients to the tamoxifen arm of the trial will be stopped. Although fulvestrant is unlikely to cause acceleration of proliferation, the same stopping rule will be applied to the fulvestrant arm as well. A mean increase of 25% in 14 patients would give an 80% confidence interval that the true mean Ki67 increase in a treatment arm is in the range of 16% to 34%.

An additional stopping rule will be implemented based on the number of patients experiencing a high level of proliferation (50% or higher). If 2 of the first 10 patients in a treatment arm experience an increase from baseline in the Ki67 proliferation index of 50% or more, then that treatment arm will be terminated.

Comparison in the Change of Proliferation Index between Fulvestrant and Tamoxifen in Cyclin D1 +, Estrogen Receptor + Breast Cancer

[name], PI

Essential Elements

#13, 09/13/2017

Patient Withdrawal from Study Participation

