Participation in the study is voluntary. Subjects may choose to withdraw at any point. They need only to inform a member of the study team. A letter of withdrawal would be the ideal procedure; however, verbal notification to any of the research study personnel would be sufficient. The request would be documented in the medical record. Already collected data will be used to aid study interpretation however, no new data would be collected.

STUDY PROCEDURES

The principal investigator and study coordinator will be responsible for data accuracy and completeness. Data will be collected electronically using Mount Sinai's secure Web-based Electronic Research Application Portal (ERAP).

The study will take place in the Dubin Breast Center at Mount Sinai Hospital, Mount Sinai West and Mount Sinai St. Luke's.

Newly diagnosed breast cancer patients with ER+ tumors in whom primary surgery is planned at Mount Sinai will be recruited during their initial consultation with surgeons at the Dubin Breast Center or Mount Sinai St. Luke's. Patients agreeable to participation in the study will have their tumor assessed for cyclin D1. Patients with cyclin D1 positive tumors will undergo the following screening procedures.

Baseline Screening Procedures:

Subjects will have the following standard blood tests, urine tests and physical exams performed as part of routine care for subjects with breast cancer:

- A medical history, which includes questions about the patient's medical and psychiatric history, current medications, and any allergies.
- Standard physical exam which includes an examination of the whole body that will include measurements of height, weight, body temperature, blood pressure and heart rate.
- Urine test, which will be utilized to perform a urine dipstick pregnancy test.
- Performance status, which evaluates how one is able to carry on one's usual activities

The results of these tests will be used to establish the subject's baseline physical condition prior to enrollment in the protocol.

Randomization to study Regimen

After giving informed consent, patients will be randomized to receive one 14-day cycle of either:

Arm A

- Fourteen (14) days of treatment with tamoxifen 20 mg orally each day

Or

Arm B

- Fulvestrant 750 mg (three (3) 5 mL injections slowly over 1-2 minutes per injection in the buttocks) on **day 1 only**

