The initial core biopsy for routine diagnosis will be performed prior to the 14 day study regimen. Then the subjects will receive 14 days of Fulvestrant or Tamoxifen as described above. After the

Comparison in the Change of Proliferation Index between Fulvestrant and Tamoxifen in Cyclin D1 +, Estrogen Receptor + Breast Cancer

[name], PI

Essential Elements

#13, 09/13/2017

14 day study regimen is complete, the subjects will move on to definitive excisional surgery, between day 15 to day 18, at Mount Sinai, which will be performed at their surgeon's discretion.

CORRELATIVE LABORATORY RESEARCH

Laboratory Determinations and Pathology Review

A study pathologist will determine Ki67 and cyclin D1 status on the initial core biopsy and the excisional surgical specimen. Scoring of the ER, PR and Her2, will be performed using the standard clinical method used for all breast cancer patients at Mount Sinai. For patients with 1+ or higher staining for Her2 on IHC, ISH will be sent. This analysis will be performed by the pathology department as part of the standard clinical management.

The intensity and distribution of cyclin D1 staining will be semiquantitatively scored using the Allred scoring method. The intensity of the immunohistochemical reaction by light microscopy will be recorded as 0 (negative) when no staining of the nuclei is seen even at high magnification, 1+ (weak) if staining is visible only at high magnification, 2+ (moderate) when staining is readily visible at low magnification and 3+ (strong) if staining is strikingly positive even at low power magnification. The extent of tumor cell nuclei showing positive staining will be scored as 0 (<10%), 1 (11-25%), 2 (26-50%), 3 (51-75%), 4 (76-90%), and 5 (>90%). Scores for intensity and extent will then be totaled to assign a tumor as having negative (0), weak (1 to 3), moderate (4 to 6), or strong (7 to 8) cyclin D1 expression as has been standardized by Reis-Filho and colleagues. A total score of greater than or equal to 5 will be used as the cut off for cyclin D1 positivity as per the retrospective study conducted by [name] and colleagues.

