Following examination by the study pathologist of the Ki67 immunohistochemically stained sections and an additional section stained with H&E, areas of viable tumor tissue within the cores will be identified, the extent of antibody staining assessed using appropriate protocols for digital image capture and analysis. It is our expectation that the cores will show considerable intratumoral heterogeneity in the extent of staining and that individual strongly staining nuclei may be interspersed among weakly or negatively stained cells. In order to address the problem of intratumoral heterogeneity, we will obtain digital images of the entire tissue section and determine the number of positively stained nuclei per 100,000 μm^2 of viable tumor tissue.

In addition, manual scoring of cyclinD1, STAT3, STAT5 and Ki67 will also be performed. The manual scoring will be performed as described previously where a score for percentage of cells stained and a score for intensity of scoring is obtained and then added to obtain an Allred score.

For the ER, we predict that pre-treatment specimens from both arms will show evidence of ER staining in the nucleus. In post-treatment specimens, the fulvestrant alone arm will show reduced nuclear staining of ER and some cytoplasmic staining of ER. The staining of ER will be assessed with the 6F11 monoclonal antibody (Vision Biosystem) as this is the antibody used clinically at this time. Intensity will be scored (0, 1+, 2+, 3+) by the level of staining in the nucleus and cytoplasm. ER will also be expressed as a percentage (0-100%) of cells staining positive within the breast tumor.

For the PR, we predict that pre-treatment specimens from both arms will show evidence of PR staining in the nucleus. In post-treatment specimens, the fulvestrant alone arm will show reduced staining of PR given the downregulation of the ER by fulvestrant. Intensity will be scored (0, 1+, 2+, 3+). PR will also be expressed as a percentage (0-100%) of cells staining positive within the breast tumor.

Tunel assay will be used to determine the percentage of cells that underwent apoptosis. Paraffin embedded sections will be stained using the apoptosis detection kit TACS-KL Basic (TA100, R&D systems Inc, Minneapolis) according to the manufacturer's protocol. Sections will be counterstained with 0.2% hematoxylin to detect intact nuclei. Our data suggest that more apoptotic cells will be detected in

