When reporting to AstraZeneca, a cover page should accompany the MedWatch/AdEERs form indicating the following:

- Investigator Sponsored Study (ISS)
- The investigator IND number assigned by the FDA
- The investigator's name and address
- The trial name/title and AstraZeneca ISS reference number

Investigative site must also indicate, either in the SAE report or the cover page, the causality of events in relation to all study medications and if the SAE is related to disease progression, as determined by the principal investigator.

Send SAE report and accompanying cover page by way of fax to AstraZeneca's designated fax line: [name]

Serious adverse events that do not require expedited reporting to the FDA need to be reported to AstraZeneca preferably using the MedDRA coding language for serious adverse events.

Comparison in the Change of Proliferation Index between Fulvestrant and Tamoxifen in Cyclin D1 +, Estrogen Receptor + Breast Cancer

[name], PI

Essential Elements

#13, 09/13/2017

This is not a blinded trial.

All SAEs have to be reported to AstraZeneca, whether or not considered causally related to the investigational product. All SAEs will be documented. The investigator is responsible for informing the IRB and/or the Regulatory Authority of the SAE as per local requirements.

Stopping Rules

Both agents in this study (tamoxifen and fulvestrant) have been used extensively in clinical practice with well-known side effects. Likewise both agents have been previously used in the pre-operative setting of a clinical trial (Young 2008). While several studies indicate that tamoxifen does not provide benefit to patients with cyclin D1 positive tumors, the study by Jirstrom et al, actually suggests that tamoxifen may accelerate the growth of tumors (Jirstrom 2005). Pre-clinical data in cell lines supports this conclusion as well. Thus, there is a concern that giving tamoxifen pre-operatively to patients with cyclin D1 positive tumors could accelerate tumor growth. This concern is however limited by two facts, first the length of the treatment regimen in this study is very short and second, tamoxifen is currently used in the neo-adjuvant setting in Europe and less frequently in the US. Please see "Removal of Patients from Therapy" section for further details.

DRUG INFORMATION

Fulvestrant

For each drug provide the following:

- Other names **Faslodex**
- Classification - type of agent: **Anti-estrogen**

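### The trial is open-label and its text does not say that the reader of post-treatment Ki67, the primary endpoint, is masked to treatment arm; coded slides and masked reading would be a cheap protection

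*Combined protocol and SAP*

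**What the plan says.** **Who reads.** Under Laboratory Determinations and Pathology Review: "A study pathologist will determine Ki67 and cyclin D1 status on the initial core biopsy and the excisional surgical specimen".

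**Blinding.** The only statement is in Reporting of serious adverse events to sponsor: "This is not a blinded trial".

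**Endpoint and analysis.** The Statistical Analysis Plan defines the primary endpoint as a change in proliferation index "as measured by the percentage of cells staining for Ki67 in each treatment arm, stratified by menopausal status". Data Analysis specifies stratified ANCOVA with "outcome variable of post treatment percentage of cells staining for Ki67 with covariate baseline percentage of cells staining for Ki67".

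**How Ki67 is read.** Correlative Laboratory Research and Correlatives/Special Studies describe two readings. One is a digital count over the whole section, expressed as positive nuclei per unit area of viable tumour. The other is manual: "manual scoring of cyclinD1, STAT3, STAT5 and Ki67 will also be performed", giving an Allred-type sum of a percentage score and an intensity score. Neither section says which reading supplies the percentage used in the primary analysis.

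**When the core is read.** Study Procedures places cyclin D1 testing before screening and randomisation ("Patients agreeable to participation in the study will have their tumor assessed for cyclin D1"). No timing is given for reading Ki67 on the core.

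**Use during the trial.** Arm-level Ki67 results feed the stopping rules. One of them is worded "if the mean change from baseline in the Ki67 proliferation index among the first fourteen patients in the tamoxifen arm"; its threshold is a rise of 25% or more. Under Removal of Patients from Therapy the consequence is that "recruitment of patients to the tamoxifen arm of the trial will be stopped". The rule applies to the fulvestrant arm as well.

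**The concern.** An open-label treatment does not require an unmasked laboratory reader. Here the endpoint is read from slides, so masking is feasible, yet the available text mentions no masking, slide coding or reading order.

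Three features of the plan make the silence matter.

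- **Stated direction.** The sample-size section hypothesises a larger Ki67 fall on fulvestrant. Removal of Patients from Therapy voices concern that tamoxifen may accelerate growth.
- **Clues to the arm.** The laboratory sections predict weaker post-treatment ER and PR staining on fulvestrant, so a reader who sees those results first could guess the arm. Part of the laboratory must know the arm anyway, because cultured cells are to receive the patient's own study drug.
- **Room for judgment.** The digital count needs viable tumour to be identified, and the manual score is a visual grade. The plan itself expects considerable heterogeneity within tumours.

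The exposed readings are those made after assignment: the excision, and any core read after randomisation. A core read before randomisation carries no arm-dependent risk. If post-treatment readings shifted by arm, the shift would pass straight into the estimated treatment difference.

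**Working it through.** **Inputs from the Statistical Analysis Plan:** difference 15 points, two-sided alpha 0.05, power 0.80, 29 per arm; SDs of 22.5 and 18.0 from the cited fulvestrant 250 mg study. The plan does not name its design SD.

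**Step 1. Reproduce the plan's sample size.**
- Pooled SD = √((22.5² + 18.0²)/2) = 20.37.
- n per arm = 2 × 20.37² × (1.960 + 0.842)² / 15² = 28.96, rounded up to 29.
- This matches the stated 29 per arm (58 in all), so 20.37 is a reasonable working SD.

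**Step 2. Effect of an assumed shift on the two-sided error.** Suppose there is no true difference and one arm's post-treatment reading is shifted by b percentage points. For an unadjusted comparison of change:
- SE = SD × √(2/29)
- error = Φ(−1.96 + b/SE) + Φ(−1.96 − b/SE)

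| SD | SE | b = 1 | b = 2 | b = 4 |
|---|---|---|---|---|
| 18.0 | 4.73 | 5.5% | 7.1% | 13.5% |
| 20.37 | 5.35 | 5.4% | 6.6% | 11.6% |
| 22.5 | 5.91 | 5.3% | 6.3% | 10.4% |

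A noncentral t check with 56 df and SD 20.37 gives 5.4%, 6.6% and 11.4%.

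**Step 3. Does ANCOVA remove the shift?** No. The shift sits in the outcome of one arm and is unrelated to baseline, so the adjusted difference carries all of it while the SE becomes smaller. With equal baseline and post-treatment variances and correlation ρ, the SE is multiplied by √((1 + ρ)/2). For assumed ρ of 0.3, 0.5 and 0.7 the SE is 4.31, 4.63 and 4.93, and the error at b = 4 is 15.3%, 13.9% and 12.8%.

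**Step 4. Effect on the stopping rules.** I assume that the rules are in percentage points and that changes are normally distributed. The stated 80% interval of 16% to 34% at n = 14 implies SE = 9/1.2816 = 7.02, so SD = 7.02 × √14 = 26.3. The shift is 4 points upward.

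| True mean change | Mean of 14 at least +25: no shift | with shift | At least 2 of 10 with +50 or more: no shift | with shift |
|---|---|---|---|---|
| −5 (planned for tamoxifen) | 0.00001 | 0.0001 | 1.3% | 2.7% |
| 0 | 0.0002 | 0.0014 | 3.1% | 5.8% |

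For example, at −5 the mean rule gives z = 30/7.02 = 4.27 without the shift and 26/7.02 = 3.70 with it.

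**Limits.** The documents give no size or likelihood for a reading shift, so b is assumed throughout. The figures apply only to a reading in percentage of cells. They do not carry over to the digital density or to the Allred score, which are in other units.

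**The case against.** The strongest reply is that this is silence, not a stated defect. The sentence on blinding sits among the instructions for reporting serious adverse events and says nothing about the laboratory. The research pharmacy initiates randomisation from its own lists, and no section gives the arm to the pathologist. Masking could be set out in a laboratory manual or in text that is not available. All of this stands as a limit on the inference. It does not supply masking, because nothing withholds the arm from the reader either.

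Whole-section imaging is a real safeguard against choosing fields. It does not cover the manual score. Nor does it settle the identification of viable tumour, which is described for the cores but not spelled out for the excision; a count per area of viable tumour needs that step on any specimen. Since the plan does not say which reading supplies the primary percentage, the digital method cannot be assumed to protect it.

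The shift sizes have no source. At 1 point the error is close to nominal. Roughly doubling it takes a uniform 4-point shift in one arm, which is 4/15 = 27% of the design difference. This also stands.

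The route through ER/PR is less direct than it may look. Laboratory Determinations and Pathology Review assigns ER and PR scoring to the pathology department by its standard clinical method, and no separate research reading by the Ki67 pathologist is established. That bears on the remedy: ordering Ki67 before a research ER/PR reading alone would leave the clinical results open to the reader, so both must be withheld.

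A reader might infer that the Ki67 results will be read unmasked, or are biased towards fulvestrant. The documents do not show either. A reader might also infer that biased reading could readily close an arm. Step 4 of the working does not support that for the mean rule, and for the 2-of-10 rule the change is small.

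**Conclusion.** The point holds as a gap worth closing, not as evidence of bias. In an open-label trial with stated directional expectations, the available text does not mask the reader of the primary endpoint, and the methods as written leave room for judgment after assignment. An arm-dependent shift would enter the treatment estimate in full, and neither randomisation nor baseline adjustment would remove it.

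The size is unknown. The illustration runs from little effect at 1 point (5.4%) to about double the nominal level at 4 points (11.6%; 10.4% to 13.5% across the two cited SDs). It rests on assumed shifts, 29 per arm, approximate normality and a reading in percentage of cells. Confidence is medium, because a masking procedure may exist outside the available text. If it does, a cross-reference from the laboratory section would close the point.

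**What to change.** Add to Correlative Laboratory Research, and repeat in Correlatives/Special Studies, wording such as:

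> Excision Ki67 slides and images, and any core slides read after randomisation, carry a study code only. The study pathologist and image analyst identify viable tumour and record all Ki67 values, including the percentage used for the primary endpoint, masked to treatment arm and without access to that patient's post-treatment ER/PR results, clinical or research, until the Ki67 values are locked. The study coordinator then links the locked values to arm for the stopping-rule checks and the analysis.

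Routine clinical ER/PR scoring proceeds unchanged; only the Ki67 reader's access to it is deferred.

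The cost is slide coding, a reading order, and a linking step before each stopping-rule check and before the analysis. No extra reader, patient procedure or change in sample size is needed. Core and excision specimens may remain recognisable as such, so masking to time point may be imperfect and bias is reduced rather than excluded.

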For the ER, we predict that pre-treatment specimens from both arms will show evidence of ER staining in the nucleus. In post-treatment specimens, the fulvestrant alone arm will show reduced nuclear staining of ER and some cytoplasmic staining of ER. The staining of ER will be assessed with the 6F11 monoclonal antibody (Vision Biosystem) as this is the antibody used clinically at this time. Intensity will be scored (0, 1+, 2+, 3+) by the level of staining in the nucleus and cytoplasm. ER will also be expressed as a percentage (0-100%) of cells staining positive within the breast tumor.

For the PR, we predict that pre-treatment specimens from both arms will show evidence of PR staining in the nucleus. In post-treatment specimens, the fulvestrant alone arm will show reduced staining of PR given the downregulation of the ER by fulvestrant. Intensity will be scored (0, 1+, 2+, 3+). PR will also be expressed as a percentage (0-100%) of cells staining positive within the breast tumor.

Tunel assay will be used to determine the percentage of cells that underwent apoptosis. Paraffin embedded sections will be stained using the apoptosis detection kit TACS-KL Basic (TA100, R&D systems Inc, Minneapolis) according to the manufacturer's protocol. Sections will be counterstained with 0.2% hematoxylin to detect intact nuclei. Our data suggest that more apoptotic cells will be detected in the cyclinD1 overexpressing tumors in response to fulvestrant compared to the tamoxifen. This analysis will therefore allow us to test this possibility in humans. Further, the analysis of the rate of apoptosis will provide an independent readout of the effect of treatments in addition to proliferation measured by Ki67.

For tumors greater than 1 cm, a small portion of the surgical specimen not needed for diagnostics will be divided: half will be frozen for subsequent RNA extraction and expression profiling, and half will be utilized for primary tissue culture.

For RNA extraction and gene expression profiling, a gene signature that distinguishes cells that are responsive to tamoxifen and those that are resistant to tamoxifen has been established using cell lines in vitro. Similarly, a gene signature of the same cells in response to fulvestrant was also determined. Using these signatures obtained in vitro, we will compare whether the same gene signature characterizes tumors that are resistant or

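### Does the laboratory text leave the primary Ki67 percentage without a source?

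*Combined protocol and SAP*

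**What the plan says.** The Endpoints list of the SAP and the later Study Design/Study Endpoints section both measure the proliferation index as the percentage of cells positive for Ki67, compared between core biopsy and surgery. Data Analysis specifies one stratified ANCOVA, with the post-treatment percentage as outcome and the baseline percentage as covariate. The sample size rests on a difference of 15 percentage points (mean reductions of 5 and 20).

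Laboratory Determinations and Pathology Review assigns the reading: "A study pathologist will determine Ki67 and cyclin D1 status on the initial core biopsy and the excisional surgical specimen". For the stained Ki67 sections, both that section and Correlatives/Special Studies have "the extent of antibody staining assessed using appropriate protocols for digital image capture and analysis". To deal with intratumoral heterogeneity they add that "we will obtain digital images of the entire tissue section and determine the number of positively stained nuclei per 100,000" square micrometres of viable tumor. Manual scoring of Ki67 follows as an additional step: a score for the percentage stained and a score for intensity, summed to an Allred score.

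The receptors are handled differently. "Scoring of the ER, PR and Her2, will be performed using the standard clinical method used for all breast cancer patients at Mount Sinai". After the intensity scale comes "ER will also be expressed as a percentage (0-100%) of cells staining positive within the breast tumor", and likewise "PR will also be expressed as a percentage (0-100%) of cells staining positive within the breast tumor". Data Analysis uses that same unit for the receptors: "The mean change in levels (expressed as a percentage of cells staining positive within the breast tumor) of ER (and PR").

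**The concern.** Read beside the ER and PR text, the Ki67 text seems to lack a link. The two receptor endpoints have a stated 0-100% value that matches what the SAP analyses. The primary marker has a count per unit area, which carries no count of unstained nuclei, and a sum of two ordinal scores. Neither converts back to a percentage. If nobody recorded the percentage at reading, slides or images would have to be read again.

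Ki67 is also read twice, digitally and manually. If each reading produced a percentage, both would satisfy the SAP wording. The trial is not blinded, and the stopping rules look at Ki67 by arm in the first 10 and first 14 patients. One could therefore worry that the primary value might be picked with results by arm in view.

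**Working it through.** **1. Which scale do the plan's own numbers use?** Inputs from the sample-size paragraph of the SAP: difference 15; SDs in the cited study 22.5 (fulvestrant 250 mg) and 18.0 (placebo); power 0.80; two-sided 0.05; 1:1 allocation. The plan does not name the SD it used, so the pooled value is inferred.

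- Pooled SD = √[(22.5² + 18.0²)/2] = √[(506.25 + 324)/2] = √415.125 = 20.37.
- n per arm = 2 × SD² × (1.960 + 0.842)² / 15² = 2 × 415.125 × 7.849 / 225 = 28.96, rounded up to 29.

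This is the stated 29 per arm (58 in total). A t-based calculation gives 29.95, rounded up to 30, with power 0.787 at 29. Effect and SD are both in percentage points of cells stained, so the sample size agrees with the endpoint definition and the ANCOVA.

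**2. Can the named outputs replace the percentage?** No.

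- *Density.* 100 positive nuclei per unit area is 100/300 = 33%, 100/500 = 20%, 100/800 = 12.5% or 100/1,000 = 10%, for assumed totals of 300, 500, 800 or 1,000 nuclei.
- *Extent score.* The bands are printed for cyclin D1 only: "The extent of tumor cell nuclei showing positive staining will be scored as 0 (<10%), 1 (11-25%), 2 (26-50%), 3 (51-75"%), and so on. If they are assumed to apply to Ki67, the widest cover 50 − 26 = 24 and 75 − 51 = 24 points.

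This would matter if the SAP analysed a density or an Allred score for Ki67. It analyses neither. A band width for one specimen is also not comparable with a 15-point difference between group means.

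**3. Can the described readings yield the percentage?** Yes.

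- *Digital.* Assessing the extent of staining is a separate step from the density sentence, and images of the whole section are kept. The percentage needs unstained tumor nuclei counted on those images.
- *Manual.* The pathologist must judge the percentage stained before assigning a score to it.

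At most 64 × 2 = 128 specimens are involved.

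**4. What would a free choice between two readings cost?** This is purely hypothetical. If either of two tests at two-sided 0.05 could count, the error rate is 1 − P(|Z₁| < 1.96 and |Z₂| < 1.96) for a bivariate normal pair with correlation r.

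| r (assumed) | Error rate |
|---|---|
| 0.95 | 6.5% |
| 0.90 | 7.0% |
| 0.80 | 7.8% |
| 0.50 | 9.1% |

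The documents give no agreement figure between digital and manual readings. The table also requires two complete percentages per specimen and a selection after results are seen. The plan describes one ANCOVA on one variable.

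**The case for a change.** The best argument for a change is that it would be cheap and would touch the primary endpoint. A few sentences modelled on the ER and PR wording would name the reading and the moment of recording, before any comparison by arm in an unblinded trial. It is true that no sentence names the source, and that the density and the Allred total cannot be turned back into a percentage.

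The rest carries less weight. The contrast with ER and PR is weaker than it looks. Their endpoint entries speak only of levels, and their laboratory text starts from an intensity scale, so a sentence giving the unit was needed there. For Ki67 the unit is already in the endpoint definition. The two halves of the worry also pull apart: if the digital step counts stained nuclei only, it yields no second percentage to compete with the manual one.

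Nor is there a clearly better reading to prescribe. Making the manual reading primary might reverse the investigators' order, since the text offers whole-section imaging as its answer to heterogeneity and adds manual scoring afterwards. Placing a tumor in a broad band also does not guarantee a percentage fine enough for ANCOVA. Without agreement data, the choice would be a preference.

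**Conclusion.** No change to the plan is called for. This is a gap in laboratory detail that the trial team can fill sensibly from the SAP. The variable, its scale, the model and the sample size are all stated and agree with one another; only the source reading is left unsaid. A team following the SAP would record a Ki67 percentage on the core biopsy and on the surgical specimen and enter the pair into the ANCOVA. The 29 per arm, the 15-point difference and the 0.05 level stay as they are.

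This conclusion assumes that the percentage is noted when specimens are read, or taken later from the retained images, and that the same reading serves both time points. If the percentage were missed, the cost would be re-reading up to 128 specimens, which is a nuisance and not a lost endpoint. The 6.5% to 9.1% error rates describe conduct that the documents do not provide for, so they do not measure a defect in this plan.
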